## Intervention Fidelity

During this pilot phase, characterizing the success and barriers encountered with trial interventions will be essential for analyzing fidelity. As a separate, but complimentary line of investigation, facilitators and barriers to support system implementation will be characterized for both HELP personnel and family members. All family members will be provided with surveys on postoperative day three (or discharge, whichever is sooner).

These surveys contain a combination of Likert-scale and open-ended questions to identify barriers to completing delirium screening and prevention activities. The substudy analysis for HELP is described in a separate, secondary application (HUM00166883). Lastly, a sensitivity analysis will be performed, which will report daily proportions – and reasons – for missing HELP- and family-based assessments (see Sensitivity Analysis and Missing Data).

## **Outcomes**

The primary outcome of this pilot trial will be the presence of delirium, defined by a positive long-form Confusion Assessment Method (CAM) screening. To complement CAM screening, delirium will also be assessed each day via validated chart review method. The following secondary outcomes will also be collected and analyzed: delirium severity (long-form CAM severity scale), new symptoms of depression or anxiety (using the Hospitalized Anxiety and Depression Scale, HADS), falls (proportion, %), length of hospital stay (days), discharge disposition (e.g., home, long-term care facility), delayed discharge due to cognitive impairment (proportion, %), incidence of any new non-surgical site infection (%), incidence of new multidrug resistant organism colonization (%), and mortality (%). Exploratory outcomes will include the incidence of positive FAM-CAM assessments (%) 30 days post-discharge, PROMIS Cognitive Function Abilities (Short Form 4a), 36-Item Short Form Survey, and 30-day readmission rates.

**Protocol Fidelity Measures:** Lastly, protocol fidelity measures will be reported for both HELP- and family-based interventions. HELP-based measures include the following: total therapeutic time spent with HELP staff during the first three postoperative days, proportion of participants visited and enrolled by HELP (%), and time to initial HELP evaluation. For family-based interventions, the following measures will be reported: cumulative time family members spent with patients, proportion of daily tasks (e.g., assistance with glasses/hearing aids, handwashing), successfully completed, length of time spent on stimulating activity, and overall agreement of the FAM-CAM with interview-rated CAM assessments.

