postoperative morning requesting early evaluation and enhanced treatment protocols. This may improve high-risk patient triage, early resource allocation, and cumulative therapeutic time spent with patients. A similar paging system could be implemented for family members and caretakers, as family-based interventions may provide additional support for patients at risk for delirium. Feasibility has been demonstrated with family-based protocols for hospitalized medical patients, with therapeutic focus on re-orientation, visual and hearing aid assistance, and conversational stimulation. Similar protocols could be adapted for surgical patients, as surgery is generally a predictable event (and thus may be amenable to familial planning), and family support may correlate with overall postoperative recovery. A recent systematic review also demonstrated that *family-performed* delirium screens demonstrated improved psychometrics compared to *family-informed* delirium screens (i.e., those not performed by family members). Thus, family members and caretakers could be recruited to actively participate in postoperative recovery by performing family-based delirium assessments and implementing therapeutic protocols. An electronic, paging-based alerting system could provide family members with reminders and alerts for conducting such a program.

The premise of this pilot proposal is thus formed by the above considerations: preliminary evidence that suggests (1) suboptimal delirium prevention resource utilization and (2) the potential role for a clinical decision support system involving HELP and family members. The primary objectives of this study are to determine whether pager-based clinical decision support systems bolster HELP- and family-based

therapeutic activities. A secondary objective will be to identify facilitators and barriers to delivering therapeutic interventions for both HELP and family members. Overall, this pilot trial will test the hypothesis that a multicomponent decision support system will improve the postoperative environment for neurocognitive and clinical recovery in older, high-risk surgical patients.

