**Interventions – Clinical Decision Support Paging System**

This proposal will build upon previous decision support systems launched by our department for reducing intraoperative awareness and delivering protective lung ventilation strategies. For participants randomized to the HELP-based support system, a single page will be sent to the on-call HELP staff during the first postoperative morning as the team begins ward rounds (Table 1). The page will request an enhanced treatment protocol, which includes HELP visitations three times daily. Therapeutic treatment will be administered during each visit per program protocols, which generally includes cognitive engagement, mealtime assistance, mobility and range of motion exercises, and assistance with visual and hearing aids. During the final evening visit, a sleep protocol will be implemented. For this protocol, HELP officials offer sleep and relaxation exercises, relaxation massages, and warm milk and/or tea.

For participants randomized to the family-based system, family members (or caretakers) will receive preoperative education on delirium (including an educational video), a folder with an informational flyer and therapeutic activities checklists, and FAM-CAM training. Suggested therapeutic activities include daily assistance with visual and hearing aids, providing assistance with drinking and mealtime assistance, handwashing, re-orientation to time and place, and cognitive stimulation activities (Supplementary Appendix). Lastly, family members will also receive a pager, and automated pages will be sent twice daily with reminders to perform these activities (Table 1). Completion of activities will then be logged daily in conjunction with unblinded members of the research team. Study activities for each group are listed in Table 2.

Days	Timing	Alphanumeric Paging Message
HELP-Based Paging System		
Postoperative day 1	Morning – 9:00 AM	Patient LAST NAME, FIRST NAME, MRN is at high-risk for postoperative delirium. Please evaluate patient as soon as possible and enroll in the enhanced treatment protocol.
Family-Based Paging System		
Postoperative days 1-3	Morning – 9:00 AM	Good morning! please complete the morning tasks listed in your folder (Morning Tasks 9:00 AM). The stimulating activity can then be performed anytime during the day. Call [contact] with questions or concerns.

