Postoperative days 1-3	Afternoon – 3:00PM	Good afternoon! please complete the afternoon tasks in your folder (Afternoon Tasks – 3:00 PM). After these are complete, perform a FAM-CAM. Make sure to also complete a stimulating activity today. Call [contact] with any questions.

**Table 1.** Real-time clinical decision support – family paging system. FAM-CAM = Family Confusion

Assessment Method

Usual Care Group (n=15)	HELP-Based System (n=15)	Family-Based System (n=15)	Combined Systems (n=15)
Preoperative Phase	Preoperative Phase	Preoperative Phase	Preoperative Phase
Standard Care	Standard Care	Preoperative delirium education, materials, FAM-CAM training	Preoperative delirium education, materials, FAM-CAM training
Intraoperative Phase	Intraoperative Phase	Intraoperative Phase	Intraoperative Phase
Standard Care	Standard Care	Standard Care	Standard Care
Postoperative Care	Postoperative Care	Postoperative Care	Postoperative Care
HELP evaluation and treatment per ward routine	HELP pager alerts	Daily family pager alerts	HELP pager alerts and associated activities
Standard care otherwise	
 
• Early evaluation request
 
• Enhanced therapeutic protocol request
 
	
 
• FAM-CAM reminders
 
• Reminders for behavioral/social support and prevention activities
 
	Family pager alerts and associated activities

**Table 2.** Participants will be randomized to one of four groups: usual care, HELP-based paging support, family-based paging support (automated pages for the first three postoperative days), or combined HELP- and family-based paging support. HELP = Hospital Elder Life Program; FAM-CAM = Family Confusion Assessment Method.

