## **Data Collection**

At Michigan Medicine, HELP data collection is standard throughout surgical and medical wards. The time at which patients are first evaluated, total therapeutic time (minutes) spent with patients, and nature of therapeutic activities (e.g., cognitive stimulation, mealtime assistance) are all collected daily and logged on computer files. Unblinded research team will have access to these logs via secured, shared drive within the Michigan Medicine network. These research personnel will review HELP logs daily and meet with HELP leadership as needed to discuss problems that may arise regarding HELP data collection and logging.

For delirium assessment, research team members will screen for delirium using the long-form CAM twice daily – once in the morning, and again in the afternoon, for the first three postoperative days. These team members will be blinded to group allocation.

Our research group has extensive experience with CAM in prior trials, and our international group has created a program for training investigators in CAM methodology with a previously high inter-rater reliability (Fleiss kappa=0.88 [95% CI 0.85 to 0.92]). Our study team members who have previously received this training will lead CAM assessment efforts for this trial. Additionally, the study PI ([name]), has received complementary CAM training from the NIH-funded (K07AG041835) Center of Excellence for Delirium in Aging: Research, Training and Educational Enhancement (CEDARTREE). For new team members not previously trained, the PI will lead an on-site training session using online long-form CAM training videos available from the Hospital Elder Life Program. Then, after each team member has successfully scored two non-delirious and two delirious patients identically – in terms of symptom recognition – with a previously trained study team member, the trainees will be considered independently trained for CAM assessment. For those enrolled in the intervention bundle, family members (or caretakers) will perform the FAM-CAM independently of the research team. FAM-CAM assessments will also be requested only daily in the afternoon.

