Descriptive statistics will be reported for secondary and exploratory outcomes. Inferential statistics will be deferred given the small sample size and pilot nature of the trial. Rigorous statistical analysis will be deferred for planned, follow-up, large-scale investigation. However, inferential statistics will be reported for fidelity measures described previously (Outcomes – Protocol Fidelity Measures). For continuous data, the Shapiro-Wilk test will be used to assess for normal distribution, and either independent t-tests or the Mann-Whitney U-test will be used, as appropriate. For categorical data, chi-squared or Fisher's exact test will be used, as appropriate. Cohen's kappa will be used to assess agreement between research-based CAM delirium assessments and FAM-CAM assessments.

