#### *Sensitivity Analysis and Missing Data*

Missing data are anticipated for multiple outcomes described in this study. For each HELP visit, cumulative therapeutic time is routinely logged, as are reasons for deferred visits. Thus, the proportion of deferred shift visits, compared to all available shifts (excluding shifts missed due to early discharge) will be reported along with associated reasons (Table 3). Nine total visits are anticipated during the first three postoperative days – daily morning, afternoon, and evening sleep visits. Similarly, missing FAM-CAM data are expected as well. Reasons for missing assessments will be presented in conjunction with barriers that family members and caretakers report for conducting FAM-CAM assessments.

HELP Program – Reasons for deferred visits	Family and Caregivers – Reasons for deferred FAM-CAM completion
HELP staff unavailable	Family unavailable for assessment
Patient engaged with other clinical staff	Patient engaged with other clinical staff
Undergoing medical testing or procedure	Undergoing medical testing or procedure
Visitors present	Not comfortable with performing evaluation
Patient sleeping	Patient sleeping
Patient declines visit	Patient refusal
Early discharge	Early discharge
Other	Other
Not specified	Not specified

**Table 3.** Anticipated Reasons for Missing Data

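### Time to initial HELP evaluation has no rule for a patient HELP never evaluates, so by default the planned test compares only evaluated patients, who are not a randomised comparison (minor, cheap to fix)

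*Combined protocol and SAP*

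**What the plan says.** The Protocol Fidelity Measures paragraph of Outcomes lists, for HELP, total therapeutic time over three days, "proportion of participants visited and enrolled by HELP (%), and time to initial HELP evaluation". Data Collection names the source, a HELP log of "The time at which patients are first evaluated, total therapeutic time (minutes) spent with patients".

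The Statistical Analysis section leaves secondary and exploratory outcomes descriptive but plans inferential tests for the fidelity measures. For continuous data, "either independent t-tests or the Mann-Whitney U-test will be used, as appropriate", guided by a Shapiro-Wilk test. Categorical data get a chi-squared or Fisher's exact test.

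On missing HELP contacts, Sensitivity Analysis and Missing Data says that "the proportion of deferred shift visits, compared to all available shifts (excluding shifts missed due to early discharge) will be reported", with reasons. Intervention Fidelity points to the same report. Table 3 foresees reasons such as "Patient declines visit", unavailable staff and early discharge.

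The page in Table 1 reads "Please evaluate patient as soon as possible and enroll in the enhanced treatment protocol". Usual care in Table 2 is "HELP evaluation and treatment per ward routine". The Introduction states: "The primary objectives of this study are to determine whether pager-based clinical decision support systems bolster HELP- and family-based" therapeutic activities.

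**The concern.** Neither named test accepts a patient without a time. Unless a rule is added, such patients drop out of the comparison. Those who remain were selected by the process the page is designed to change, so the comparison no longer rests on randomisation. A page that brings in extra patients late in the window could look slower than usual care although it delayed nobody.

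Time zero is also not stated. End of surgery, arrival on the ward and the 09:00 page on postoperative day 1 give different times even if every patient is evaluated.

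This is the one fidelity measure of how early HELP arrives. Bolstering HELP activity is a primary objective, and Dissemination looks to better HELP evaluation before a larger trial, though it sets no threshold. The comparison with 2018 HELP records in Strengths and Limitations meets the same gap.

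**Working it through.** **No planned figure to reproduce.** The only power statement (above 80%, 30 per group, 20% baseline, 15-point difference) concerns delirium. None is given for this measure.

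**Step 1: what covers a never-evaluated patient?**
- Data Collection: a time exists only if an evaluation took place.
- Statistical Analysis: two tests for continuous data, neither of which handles censoring.
- Intervention Fidelity, and Sensitivity Analysis and Missing Data: counts of deferred visits and reasons, with no instruction for the test.
- Tolerance of missing data in the estimating-equation models, and intention-to-treat (in the pragmatic-explanatory section), are stated for the primary analysis only.

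Nothing supplies a value, rank, censoring rule or analysis set.

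**Step 2: how selected is the evaluated group?** Let p0 and p1 be the proportions evaluated without and with the page, and suppose the page takes evaluation away from nobody. Of the paged patients evaluated, the share who would not have been evaluated otherwise is (p1 − p0)/p1. With 30 per group and assumed values:

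| p0, p1 | Evaluated | Share without counterpart |
|---|---|---|
| 45%, 90% | 13.5 v 27 | 0.45/0.90 = 50% |
| 60%, 90% | 18 v 27 | 0.30/0.90 = 33% |
| 80%, 90% | 24 v 27 | 0.10/0.90 = 11% |

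**Step 3: can it mislead?** Suppose the page delays nobody but adds patients. Assume a median of 8 h for those reached anyway, and a median of 30 h (all after 24 h) for late-added patients. With 3,000 simulated trials at 30 v 30, two-sided 5%, the evaluated-only Mann-Whitney test is significant with paging slower (nominal 2.5%) as follows:

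| p0, p1 | All added late | 75% | 50% | 25% | None |
|---|---|---|---|---|---|
| 45%, 80% | 47.8% | 27.5% | 14.9% | 6.3% | 2.4% |
| 60%, 85% | 27.4% | 17.4% | 10.5% | 4.0% | 2.5% |
| 80%, 90% | 8.1% | 6.7% | 4.3% | 3.3% | 2.1% |

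The problem needs low usual-care reach and at least about half of the added patients reached late. The first column is a constructed worst case.

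**Step 4: does an all-randomised test gain power?** The window is 09:00 on day 1 to the end of day 3: 15 + 24 + 24 = 63 h. Times among evaluated patients follow a truncated exponential with the stated median, and never-evaluated patients are held at 63 h. The table gives the chance that at least one planned test (evaluated-only Mann-Whitney or Fisher on the proportion evaluated) is significant, the same with each planned test at 2.5%, and a single log-rank test, at 30 v 30.

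| Medians | p0, p1 | Either test at 5% | Each at 2.5% | Log-rank |
|---|---|---|---|---|
| 24 v 12 h | 60%, 90% | 86–87% | 75–76% | 94–95% |
| 24 v 12 h | 70%, 90% | 71% | 58% | 80% |
| 24 v 12 h | 80%, 90% | 62% | 48% | 56% |
| 24 v 6 h | 60%, 90% | 99% | 98% | 99% |
| 24 v 6 h | 70%, 90% | 99% | 97% | 95% |
| 24 v 6 h | 80%, 90% | 99% | 97% | 87–88% |

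With 1,500 to 3,000 trials per cell, the simulation standard error is at most √(0.25/1,500) = 1.3 points. Two unadjusted tests have a combined null rate of 6.1% to 7.5%, hence the 2.5% column. The direction depends on the assumed speed of response, and the documents do not settle it.

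**The case against.** The strongest reply is that the plan already gives a legitimate two-part description: the proportion visited, tested in all randomised patients, beside the time among those reached, with missed visits and reasons reported. That stands in large part. The proportion test exposes any imbalance in reach and recovers most of the information, but it does not turn the timing comparison into a randomised one.

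Second, a log-rank test can cost power. A page sent at 09:00 asking for prompt evaluation may well produce a same-day response, and with high usual-care reach the planned pair then does better (Step 4). This stands, and it removes power as a reason for the change.

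Third, a log-rank analysis needs rules of its own for early discharge, for evaluations before time zero and for which groups are compared. This is right, and the fix supplies them.

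Three stronger readings are tempting but unsupported. A reader might infer that the plan excludes never-evaluated patients. It does not say so: exclusion is the default where nothing is stated, and the wording on choice of test leaves some room to rank them. A reader might take the Introduction's figure of under 50% to mean that half of usual-care patients are never evaluated. That figure is formal enrolment by the end of day 2 among 2018 patients, not evaluation by day 3 in this trial. Routine HELP care, the exclusion of planned ICU admissions and an anticipated stay of at least 72 hours are compatible with high reach. A reader might also expect the timing result to reverse; Step 3 shows how particular the conditions for that are.

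**Conclusion.** The gap is real, minor and cheap to close. As written, the timing test would by default compare a post-randomisation subset, and it can mislead if usual-care reach is low. The size cannot be fixed from the documents: every reach fraction and time above is an assumption, and the effect vanishes as reach becomes equal or nearly complete in both groups. The case for change rests on freedom from selection bias, not on power. The primary delirium analysis is unaffected. So is total therapeutic time, where an unvisited patient contributes 0 minutes.

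**What to change.** Add a few sentences to the fidelity-measure paragraph of Statistical Analysis:

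- Analyse time to initial HELP evaluation in all randomised patients, with cumulative incidence curves and a log-rank test.
- Use one time zero that applies equally to all arms, for example 09:00 on postoperative day 1, and end the window at the close of day 3.
- Count evaluations before time zero as events at time zero. Keep never-evaluated patients as not evaluated to the end of the window.
- State one rule for early discharge, for example censoring at discharge, with a sensitivity analysis that holds such patients to the end of the window.
- State the groups compared. HELP-page (HELP and combined arms, 15 + 15 = 30) against no HELP-page (usual care and family arms, 30) fits the pooling in the power calculation.
- Keep the planned test of the proportion visited and read it with the timing result. Report evaluated-only times as descriptive.
- Use the same definition for the 2018 records.

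No new trial data are needed, because first-evaluation times are already logged. The costs are in interpretation and power. The result combines speed with reach. It may lose power when the page mainly speeds evaluation and usual-care reach is high. It is also weaker than the proportion test when the page only adds late-reached patients (58% v 73% at 45% and 80% reach; 33% v 49% at 60% and 85%), which is why the proportion test must stay.

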## **Data Collection**

At Michigan Medicine, HELP data collection is standard throughout surgical and medical wards. The time at which patients are first evaluated, total therapeutic time (minutes) spent with patients, and nature of therapeutic activities (e.g., cognitive stimulation, mealtime assistance) are all collected daily and logged on computer files. Unblinded research team will have access to these logs via secured, shared drive within the Michigan Medicine network. These research personnel will review HELP logs daily and meet with HELP leadership as needed to discuss problems that may arise regarding HELP data collection and logging.

For delirium assessment, research team members will screen for delirium using the long-form CAM twice daily – once in the morning, and again in the afternoon, for the first three postoperative days. These team members will be blinded to group allocation.

Our research group has extensive experience with CAM in prior trials, and our international group has created a program for training investigators in CAM methodology with a previously high inter-rater reliability (Fleiss kappa=0.88 [95% CI 0.85 to 0.92]). Our study team members who have previously received this training will lead CAM assessment efforts for this trial. Additionally, the study PI ([name]), has received complementary CAM training from the NIH-funded (K07AG041835) Center of Excellence for Delirium in Aging: Research, Training and Educational Enhancement (CEDARTREE). For new team members not previously trained, the PI will lead an on-site training session using online long-form CAM training videos available from the Hospital Elder Life Program. Then, after each team member has successfully scored two non-delirious and two delirious patients identically – in terms of symptom recognition – with a previously trained study team member, the trainees will be considered independently trained for CAM assessment. For those enrolled in the intervention bundle, family members (or caretakers) will perform the FAM-CAM independently of the research team. FAM-CAM assessments will also be requested only daily in the afternoon.

Depression and anxiety measures will take place both at preoperative baseline and during postoperative day three (or day of discharge, whichever is sooner). For assessment of falls, study team members will ask about fall occurrences during each study visit, and the medical record will also be reviewed for any falls during the study period. Additional clinical secondary outcomes described will be collected from the electronic medical record. On postoperative day three, for patients not randomized to

the family-support groups, the research team will ask family members about cumulative time spent with patients, and any interactive activities performed, during the first three postoperative days for comparison to family-based intervention groups.

Finally, research data recorded on paper will be stored in participant research records that will be located in locked cabinets in the Department of Anesthesiology at Michigan Medicine. Electronic data will be de-identified and stored online using the REDCap electronic research database, which resides on a secured, password-protected network managed by the Michigan Institute of Clinical and Health Research.

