### Inclusion criteria:

- Age  $\geq 70$  years of age

- Major non-cardiac, non-intracranial neurologic, and non-major vascular surgery, as defined by work-related value units suggestive of high surgical complexity.
- Anticipated length of hospital stay at least 72 hours
- At least one family member, or caretaker, available on each of the three first postoperative days for trial operations

Exclusion criteria:

- Emergency surgery
- Severe cognitive impairment (precluding ability to perform delirium assessments)
- Planned post-operative ICU admission (HELP unavailable in the ICU)
- Non-English speaking

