Considerable limitations are also worth discussion. The statistical powering strategy crucially assumes there is no interaction between the interventions (e.g., HELP- and family-based support), which may not be the case. However, this pilot phase will help generate effect size and feasibility data for refining future protocols and power calculations. Next, both HELP officials and family members may be subject to the Hawthorne effect. That is, individuals may modify their behavior under study conditions. Both HELP officials and family members may rigorously perform study protocols knowing that performance is being monitored. As such, protocol effectiveness will likely decrease in non-research settings. For the HELP program, performance measures will be compared to historical controls (2018 HELP records) to mitigate this effect. Family members of patients not randomized to family-based support interventions may still elect to spend more time with patients after learning about the trial and proceeding with enrollment. To assess for latent family support in the control groups, the research team will ask family members about time and activities with patients for comparisons to structured family-based support allocation groups. This will be assessed on the afternoon of postoperative day three, at the end of the inpatient study window, to avoid inadvertent introduction of study-related family support interventions. Additionally, while family members will receive basic training and education on FAM-CAM administration, they will not receive rigorous training for assessing reliability or accuracy. Such training could be pursued in a follow-up trial. Lastly, only patients with family members and/or caretakers – who will be available for the first three days of hospitalization – will be eligible for the trial. Thus, patients without such social support will be ineligible. These eligibility criteria thus exclude a group of

patients who may be particularly vulnerable to delirium (i.e., less social support) and reduce trial pragmatism.

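### Family time and activities are captured differently in the arms with and without family paging, so a between-arm difference may partly reflect how they were measured

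*Combined protocol and SAP*

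**What the plan says.** **Arms without family paging (usual care and HELP only).** Under Data Collection, on postoperative day three, "the research team will ask family members about cumulative time spent with patients, and any interactive activities performed, during the first three postoperative days". The same sentence limits this to patients outside the family-support groups and gives its purpose as comparison with those groups. Strengths and Limitations repeats the purpose and explains the timing: "This will be assessed on the afternoon of postoperative day three, at the end of the inpatient study window, to avoid inadvertent introduction" of family support by the study itself.

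**Arms with family paging (family only and combined).** The Interventions section gives families checklists and twice-daily pages, and says: "Completion of activities will then be logged daily in conjunction with unblinded members of the research team". The text does not say that the day-three question is asked here, or how total family time is obtained.

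**Use of the data.** Protocol Fidelity Measures, under Outcomes, lists "cumulative time family members spent with patients" first among the family measures. Statistical Analysis defers inference for secondary and exploratory outcomes, but "inferential statistics will be reported for fidelity measures described previously", with a t-test or Mann-Whitney test for continuous data. It does not name the groups to be compared.

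**A contact that all arms share.** Intervention Fidelity says: "All family members will be provided with surveys on postoperative day three (or discharge, whichever is sooner"). The stated content of that survey is barriers to screening and prevention activities, not time.

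**The concern.** The Introduction makes it a primary objective to find out whether paging increases HELP-based and family-based therapeutic activity. Family time is the family measure that the plan expressly sets against the non-paged arms. If the data source changes with allocation, the paging effect and the recording effect are confounded, and no analysis of the collected data can separate them. A daily record made with staff and a single recall over three days can differ in mean and in spread. The resulting error could create an apparent effect or hide a real one.

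The HELP half of the objective does not have this problem. Data Collection states that "HELP data collection is standard throughout surgical and medical wards", with therapeutic minutes logged daily, so HELP time has one source in every arm.

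What is at stake is the evidence on whether family paging changes family behaviour, which bears on whether the family component goes into the larger trial. The primary outcome is not at stake, because CAM assessors are blinded to allocation.

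**Working it through.** The plan states no figure on this point, so the main check is a comparison of the text.

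| Item | Usual care and HELP only | Family only and combined |
|---|---|---|
| Activities | One recall question, day three | Daily log with unblinded staff |
| Total family time | Same recall question, day three | Not stated |
| Prompting | None intended before day three | Training, checklists, two pages a day |
| Fallback for discharge before the day-three question | Not stated | Question not asked |

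For activities, the source differs by arm on the face of the text. For total time, one side has a stated method and the other has none. No instrument common to the four arms is described.

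The missing discharge fallback is minor. Eligibility requires "Anticipated length of hospital stay at least 72 hours", which limits how many families it affects.

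**Illustration of size.** Inputs from the documents are 15 patients per arm, hence 15 vs 15 for one paged arm against usual care, or 15 + 15 = 30 vs 30 when arms are pooled by family paging. The 5% level is the one given for the delirium power calculation. Assumptions are that this level also applies to the fidelity tests, that the tests are two-sided, that data are normal with equal SD, that true family time is equal, and that the recording method shifts one side by d SD.

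The chance of a significant t-test is P(|T| > t_crit), with T noncentral t, 2n − 2 degrees of freedom (58 or 28) and noncentrality λ = d × √(n/2). For n = 30 and d = 0.4, λ = 0.4 × √15 = 1.549. For n = 15 and d = 0.4, λ = 0.4 × √7.5 = 1.095. The Mann-Whitney figures come from 20,000 simulated normal data sets per setting.

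| Assumed d | λ, 30 vs 30 | t-test | Mann-Whitney | λ, 15 vs 15 | t-test | Mann-Whitney |
|---|---|---|---|---|---|---|
| 0.2 | 0.775 | 11.9% | 11.1% | 0.548 | 8.3% | 7.5% |
| 0.4 | 1.549 | 33.2% | 31.6% | 1.095 | 18.5% | 17.0% |
| 0.6 | 2.324 | 62.8% | 59.3% | 1.643 | 35.5% | 32.3% |

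Over a wider range, d = 0.1 gives 6.7% (30 vs 30) and 5.8% (15 vs 15), and d = 1.0 gives 96.8% and 75.3%. The nominal rate is 5%.

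The same table shows masking, because only the net difference matters. A true gain of 0.6 SD would be detected in 62.8% of trials at 30 vs 30. If the recording method shifts the result by 0.4 SD the other way, the net difference is 0.6 − 0.4 = 0.2 SD and detection falls to 11.9%.

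**The case against.** The strongest case against has four parts.

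- **The asymmetry is deliberate.** The control question is a check for latent family support, and it comes late so as not to prompt those families. Daily logging in control arms would itself prompt them, and the paged arms need a log to measure adherence. This explains when control families are asked. It does not explain why paged families, who are already prompted, are left out of the same question.
- **The Supplementary Appendix is not among the documents.** Its checklist may have a time field. Outcomes also lists the length of the stimulating activity, so some duration must be captured in the paged arms. This stands as a limit on what can be said: for total time, the difference in source is inferred. But a time field on a daily checklist would still set a daily record against a three-day recall.
- **The test at risk is not spelled out.** Statistical Analysis names no groups, and Data Collection promises a comparison rather than a test. That is correct. A two-sample test of family time is the natural reading, and a descriptive comparison would be confounded in the same way.
- **The percentages are only the t-test power function at assumed shifts.** That is also correct. They show how sensitive a trial of this size is to a method difference and are no estimate of what will happen.

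It is also true that feasibility can be judged largely from completion within the paged arms, FAM-CAM agreement and the barrier surveys, none of which depend on this comparison.

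**Conclusion.** The concern holds. Followed as written, the plan uses different sources by allocation for family activities and very probably for family time, on a measure tied to a primary objective and marked for inferential testing. A between-arm difference could not be attributed to paging alone.

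The size and direction of any bias are unknown. Under assumed shifts of 0.2 to 0.6 SD with no true difference, the false-positive rate would be about 12% to 63% at 30 vs 30 and about 8% to 35% at 15 vs 15, and shifts in the other direction would hide a real gain. These figures rest on the assumptions listed in the check, including pooling by family paging, which the plan does not state for fidelity measures.

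The primary delirium outcome and the HELP time measure are not affected. The change is recommended because it is cheap and protects a comparison the plan sets out to make.

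**What to change.** - Ask families in all four arms the same question on time and activities, in the same form and mode, on the afternoon of day three or at discharge if sooner. Place it alongside the day-three survey that every family already receives. Asking at the end of the window keeps the protection against prompting control families.
- Name that common measure as the one used for between-arm comparisons, and name the groups compared.
- State how family time is recorded in the paged arms, and keep the daily logs for adherence within those arms.
- State as a limitation that training, pages and checklists may still aid or colour paged families' recall.

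The cost is one or two items at an existing contact for 60 families, of whom about 30 are newly asked, plus one or two sentences each in Data Collection and Statistical Analysis. The drawbacks are that recall is less precise than a log, and that the change removes the difference in instrument but not all differential reporting, since families cannot be blinded to the family intervention.
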